6.1. Inclusion Criteria

Patients are eligible for inclusion in the study only if they meet all of the following criteria at screening and/or at other visits prior to randomization, when indicated:

Disease Characteristics

- [1] Have had T2DM for at least 1 year;
- [2] Treated with diet and exercise and a stable dose of metformin (3 months prior to study entry) with or without 1 additional OAM other than metformin; doses of metformin will be considered stable if all prescribed doses for the previous 3 months were ± 850 mg from the most commonly prescribed dose; allowed OAMs, in combination with metformin are DPP-IV inhibitors, SGLT-2 inhibitors, acarbose, glinides and sulfonylureas; in patients with established cardiovascular disease who are treated with SGLT-2 inhibitors, this therapy should not be discontinued and therefore, these patients will NOT be eligible for participation in the trial.
- [3a] Have a hemoglobin A1c value at screening of $\ge 6.5\%$ and $\le 9.0\%$ (48 to 75 mmol/mol), if on metformin only;
- [3b] Have a hemoglobin A1c value at screening of $\ge 6.0\%$ and $\le 8.5\%$ (42 to 69 mmol/mol), if on metformin and 1 more allowed OAM;

Patient Characteristics

- [4] Male or female patients aged 18 to 70 years, inclusive
- [4a] Male patients:

- Men, regardless of their fertility status, with nonpregnant women of childbearing potential (WOCBP) partners must agree to either remain abstinent (if this is their preferred and usual lifestyle) or use condoms as well as 1 additional highly effective (less than 1% failure rate) method of contraception (such as combination oral contraceptives, implanted contraceptives, or intrauterine devices) or effective method of contraception (such as diaphragms with spermicide or cervical sponges) for the duration of the study and until their plasma concentrations are below the level that could result in a relevant potential exposure to a possible fetus, predicted to be 90 days.
 - Men and their partners may choose to use a double-barrier method of contraception. (Barrier protection methods without concomitant use of a spermicide are not an effective or acceptable method of contraception. Thus, each barrier method must include use of a spermicide. It should be noted, however, that the use of male and female condoms as a double-barrier method is not considered acceptable due to the high failure rate when these barrier methods are combined).
 - Periodic abstinence (e.g., calendar, ovulation, symptothermal, postovulation methods), declaration of abstinence just for the duration of the study, and withdrawal are not acceptable methods of contraception.
- Men with pregnant partners should use condoms during intercourse for the duration of the study and until the end of estimated relevant potential exposure in WOCBP (90 days).
- Men must agree to refrain from sperm donation for the duration of the study and until their plasma concentrations are below the level that could result in a relevant potential exposure to a possible fetus, predicted to be 90 days following last dose of study drug.
- Men who are in exclusively same-sex relationships (as their preferred and usual lifestyle) are not required to use contraception.

[4b] Female patients:

- Women of childbearing potential who are abstinent (if this is complete abstinence, as their preferred and usual lifestyle) or in a same-sex relationship (as part of their preferred and usual lifestyle) must agree to either remain abstinent or stay in a same-sex relationship without sexual relationships with males. Periodic abstinence (e.g., calendar, ovulation, symptothermal, postovulation methods), declaration of abstinence just for the duration of a study, and withdrawal are not acceptable methods of contraception.
- Otherwise, WOCBP participating must agree to use effective contraception, (see contraception guidance below), for the entirety of the study. Contraception must continue following completion of study drug administration for 30 days.

- Women of childbearing potential participating must test negative for pregnancy prior to initiation of treatment as indicated by a negative serum pregnancy test at the screening visit followed by a negative urine pregnancy test within 48 hours prior to exposure and at other times as specified in Section 2 (Schedule of Activities).
- Two forms of effective contraception, where at least 1 form is highly effective (less than 1% failure rate, such as combination oral contraceptives, implanted contraceptives, or intrauterine devices) will be used. Effective contraception (such as male or female condoms with spermicide, diaphragms with spermicide, or cervical sponges) may be used as the second therapy. Barrier protection methods without concomitant use of a spermicide are not a reliable or acceptable method. Thus, each barrier method must include use of a spermicide (that is, condom with spermicide, diaphragm with spermicide, female condom with spermicide). It should be noted that the use of male and female condoms as a double-barrier method is not considered acceptable due to the high failure rate when these methods are combined.
- Women who are not of childbearing potential may participate and include those who are:
 - Infertile due to surgical sterilization (hysterectomy, bilateral oophorectomy, or tubal ligation), congenital anomaly such as mullerian agenesis, or
 - Postmenopausal – defined as either
 - i. A woman at least 50 years of age with an intact uterus, not on hormone therapy, who has had either
 - a) cessation of menses for at least 1 year, or
 - b) at least 6 months of spontaneous amenorrhea with a follicle-stimulating hormone >40 mIU/mL; or
 - ii. A woman at least 55 years of age not on hormone therapy, who has had at least 6 months of spontaneous amenorrhea; or
 - iii. A woman at least 55 years of age with a diagnosis of menopause prior to starting hormone replacement therapy.

[5] Have a body mass index between 23.0 kg/m² and 45.0 kg/m², inclusive, at screening; are of stable weight ($\pm 5\%$) >3 months prior to screening; and agree not to initiate an intensive diet and/or exercise program during the study with the intent of reducing body weight other than lifestyle and dietary measures for diabetes treatment;

[6] Have venous access sufficient to allow for blood sampling as per the protocol.

Informed Consent

- [7] Are reliable and willing to make themselves available for the duration of the study and are willing to follow study procedures;
- [8] Have given written informed consent approved by Lilly and the ethical review board (ERB) governing the site.

6.2. Exclusion Criteria

Patients will be excluded from study enrollment if they meet any of the following criteria at screening and/or at other visits prior to randomization, when indicated:

Primary Study Condition - Diabetes Related

- [9] Have type 1 diabetes mellitus;
- [10] Have had more than 1 episode of severe hypoglycemia, as defined by the American Diabetes Association criteria, within 6 months before screening or has a history of hypoglycemia unawareness or poor recognition of hypoglycemic symptoms; any patient that cannot communicate an understanding of hypoglycemic symptoms and the appropriate treatment of hypoglycemia prior to the first dose of study drug should also be excluded;
- [11] Have had 1 or more episodes of ketoacidosis or hyperosmolar state/coma requiring hospitalization within the 6 months prior to screening;
- [12] Have a history of proliferative retinopathy or maculopathy as determined by the investigator based on a recent (<6 months) ophthalmologic examination;
- [13] Impaired renal estimated glomerular filtration rate <60 mL/min/1.73 m² calculated by Chronic Kidney Disease-Epidemiology. One retest may be performed in case of an initial result <60 mL/min/1.73 m². The highest value from the 2 tests will be accepted.

Prior/Concomitant Therapy - Glucose-Lowering Medications

- [14] Have taken any glucose-lowering medications other than those indicated in Inclusion Criterion [2] during the last 3 months before screening or during the screening/lead-in period; short-term use of insulin (<14 days) for treatment of acute conditions is allowed in the 3-month period prior to entry and after randomization (see Section 7.7 Concomitant Therapy)

Medical Conditions - General

- [15] Have a history or current cardiovascular, respiratory, hepatic, renal, GI, endocrine, hematological, or neurological disorders capable of significantly altering the absorption, metabolism, or elimination of drugs; of constituting a risk when taking the IP; or of interfering with the interpretation of data
- [16] Have acute or chronic pancreatitis or a history of acute idiopathic pancreatitis; patients who had cholecystolithiasis and/or cholecystectomy in the past, with no long-term complications, are eligible for participation;

- [17] Have a known clinically significant gastric emptying abnormality (e.g., severe diabetic gastroparesis or gastric outlet obstruction) or have undergone gastric bypass (bariatric) surgery or restrictive bariatric surgery (e.g., Lap-Band®);
- [18] Have a personal or family history of medullary thyroid carcinoma (MTC), multiple endocrine neoplasia syndrome type 2 (MEN 2), or calcitonin ≥ 20 pg/mL ($\geq 5,85$ pmol/L) at screening;
- [19] Have had acute myocardial infarction, congestive heart failure New York Heart Association Class III or IV, history of or suspected ischemic heart disease, and/or cerebrovascular accident (stroke [including transient ischemic attack]);
- [20] Have findings in the 12-lead ECG at screening that, in the opinion of the investigator, may increase the risks of potentially clinically relevant worsening associated with participation in the study;
- [21] Have an active or untreated malignancy or have been in remission from a clinically significant malignancy (other than basal or squamous cell skin cancer, *in situ* carcinomas of the cervix, or *in situ* prostate cancer) for <5 years prior to screening;
- [22] Have evidence of human immunodeficiency virus (HIV) and/or positive HIV antibodies;
- [23] Have evidence of hepatitis B or positive hepatitis B surface antigen and/or evidence of hepatitis C virus (HCV) or hepatitis C antibody at screening. Patients with a previous diagnosis of HCV who have been treated with antiviral therapy and achieved a sustained virological response may be eligible for inclusion in the study, provided they have no detectable HCV RNA on the screening HCV polymerase chain reaction test. A sustained virological response is defined as an undetectable HCV RNA level 24 weeks after completion of a full, documented course of an approved antiviral therapy for HCV.

Patients who have spontaneously cleared HCV infection, defined as (1): a positive HCV antibody test and (2): a negative HCV RNA test, with no history of anti-HCV treatment, may be eligible for inclusion in the study, provided they have no detectable HCV RNA on screening for this study.
- [24] Have serum aspartate aminotransferase (AST) or alanine aminotransferase (ALT) $>2.5\times$ the upper limit of normal (ULN) or total bilirubin level (TBL) $>1.5\times$ ULN;
- [25] Have had a blood donation of 500 mL or more in the last 3 months or any blood donation within the last month prior to screening;
- [26] Have had a blood transfusion or severe blood loss within the last 3 months or have known hemoglobinopathy, hemolytic anemia, sickle cell anemia, or have a hemoglobin value <11 g/dL (males) or <10 g/dL (females), or any other condition known to interfere with hemoglobin A1c measurement;

- [27] Have a history of drug or alcohol abuse; and/or smoke >10 cigarettes per day or the equivalent; or are unable or unwilling to refrain from nicotine 4 hours before each CRU admission and outpatient visit, and throughout the duration of each CRU visit;
- [28] Have an average weekly alcohol intake that exceeds 21 units per week (males) and 14 units per week (females) (1 unit = 12 oz or 360 mL of beer; 5 oz or 150 mL of wine; 1.5 oz or 45 mL of distilled spirits), or are unwilling to stop alcohol consumption 24 hours before each CRU admission and outpatient visit, and throughout the duration of each CRU visit;
- [29] Have evidence of significant active neuropsychiatric disease as determined by the investigator;

Prior/Concomitant Therapy - General

- [30] Have been treated with prescription drugs that promote weight loss (e.g., sibutramine, mazindol, phentermine, lorcaserin, naltrexone/bupropion, liraglutide) or similar other body weight loss medications, including over-the-counter medications (e.g., alli®) within 3 months prior to screening or between screening and randomization;
- [31] Have received chronic (lasting >14 consecutive days) systemic glucocorticoid therapy (excluding topical, intra-articular, and inhaled preparations) within 1 month before screening, or between screening and randomization;
- [32] Have received treatment with a drug that has not received regulatory approval for any indication within 1 month prior to screening; if the previous study drug has a long half-life, 3 months or 5 half-lives (whichever is longer) should have passed.

Prior/Concurrent Clinical Trial Experience

- [33] Are persons who have previously completed or withdrawn from this study;
- [34] Have previous exposure or known allergies to tirzepatide or related compounds, or have an intolerance to GLP-1RAs;
- [35] Are currently enrolled in a clinical study involving an IP or any other type of medical research judged not to be scientifically or medically compatible with this study.

Other Exclusions

- [36] Are investigative site personnel directly affiliated with this study and their immediate families. Immediate family is defined as a spouse, parent, child, or sibling, whether biological or legally adopted;
- [37] Are Eli Lilly and Company, University of Graz, or Covance employees.;
- [38] Are deemed unsuitable by the investigator for any other reason.

6.3. Lifestyle and/or Dietary Requirements

Throughout the study, patients may undergo medical assessments and review of compliance with requirements described in this section before continuing in the study.

6.3.1. Meals and Dietary Restrictions

During the study, patients should follow their usual dietary regimen that is a part of their diabetes management, as agreed with the investigator or his/her designee. For certain assessments, the patients will be required to attend the CRU in a fasting state, after an overnight fast lasting at least 8 hours, for safety laboratory tests and hormone assessments, or for longer during the hypoglycemic clamp.

6.3.2. Caffeine, Alcohol, and Tobacco

No alcohol will be allowed at least 24 hours before each CRU admission and outpatient visit and throughout the duration of each CRU visit. Caffeine consumption will not be permitted during the hypoglycemic clamp visits. Between CRU visits, weekly alcohol should not exceed 21 units per week for males and 14 units per week for females (a unit is defined in Section 6.2 Exclusion Criteria). No nicotine use will be allowed at least 4 hours before each CRU admission and outpatient visit and throughout the duration of each CRU visit. While not resident in the CRU, nicotine use must be no more than 10 cigarettes or equivalent per day.

6.3.3. Activity

Patients will be advised to maintain their regular levels of physical activity/exercise during the study. No intense physical activity will be allowed for at least 48 hours before each CRU admission. When certain study procedures are in progress at the CRU, patients may be required to remain recumbent or sitting.

6.4. Screen Failures

Screening may include re-assessment of some parameters (for example, vital signs and ECGs) and laboratory tests at the discretion of the investigator. Individuals who do not meet the criteria for participation in this study (screen failure) may be re-screened up to 1 additional time. Additionally, individuals who had been rescreened once and marked as screen failures during the halt in enrolment due to the COVID-19 pandemic may be allowed to be rescreened up to 1 more time. The interval between re-screenings should be at least 2 weeks. When re-screening is performed, the individual must sign a new ICF and will be assigned a new site screening number. If patients are rescreened, they will be assigned a new screening number. Patient numbers/enrollment numbers are assigned at Visit 2 to ensure only eligible patients enter the study.

7. Treatment

7.1. Treatment Administered

This study involves a crossover comparison of tirzepatide 15 mg and placebo administered SC QW for 12 weeks per treatment period with a washout of at least 8 weeks between treatment periods.

Table GPHG.2 shows the treatment regimens and dose escalation plan.

Table GPHG.2. Dose Titration

	Dose Titration Schemes			
Treatment	Week 1-2	Week 3-4	Week 5-8	Week 9-12
Tirzepatide	1 × 2.5-mg PFS	1 × 5-mg PFS	1 × 10-mg PFS	1 × 15-mg PFS
Placebo	1 × PFS	1 × PFS	1 × PFS	1 × PFS

Abbreviations: PFS = prefilled syringe.

All treatments will be administered QW, either at the CRU or self-administered by the patient. All injections will be administered into the SC tissue of the abdominal wall. Injection sites will be alternated weekly between 4 sites (right and left upper quadrants and right and left lower quadrants) of the abdominal wall.

The investigator or designee is responsible for:

- explaining the correct use of the IP to the patient and site personnel
- verifying that instructions are followed properly
- maintaining accurate records of IP dispensing and collection
- and returning all unused medication to Lilly or its designee at the end of the study

Note: In some cases, sites may destroy the material if, during the investigative site selection, the evaluator has verified and documented that the site has appropriate facilities and written procedures to dispose of clinical materials.

The site will be instructed to discard used medications according to local regulations.

7.1.1. Packaging and Labeling

All strengths of tirzepatide will be provided as prefilled syringes (PFS) containing 0.5-mL solution and provided in individual cartons to be dispensed. Placebo will also be provided as matching 0.5-mL PFS.

The IP will be labeled according to the country's regulatory requirements.

7.1.2. Medical Devices

The medical devices provided for patient use in the study (SMPG) are commercially available glucose meters and lancets.

7.2. Method of Treatment Assignment

Patients who meet all criteria for enrollment will be randomized to receive either tirzepatide 15 mg followed by placebo or vice versa. Assignment to treatment sequence will be determined by a randomization table with treatment codes.

7.2.1. Selection and Timing of Doses

The doses will be administered QW according to the randomization schedule, on the same day of the week and at approximately the same time of the day. Visit windows should be used for dosing only when the patient is unable to attend the CRU on the scheduled day. The actual time of all dose administrations will be recorded in the patient's electronic case report form (eCRF). If a patient does not receive her/his planned treatment dose on the scheduled day, the dose should be administered as soon as possible and at least 72 hours prior to the next scheduled dose. If the remaining time to the next scheduled dose is less than 72 hours, the dose will not be administered and will be considered a missed dose.

7.3. Blinding

This study is a patient- and investigator-blind study. Blinding will be maintained throughout the conduct of the study as described in the separate Blinding Plan.

If a patient's study treatment assignment is unblinded, the patient must be discontinued from the study, unless the investigator obtains specific approval from a Lilly clinical pharmacologist (CP) or clinical research physician (CRP) for the patient to continue in the study. During the study, emergency unblinding should occur only by accessing the patient's emergency code.

In case of an emergency, the investigator has the sole responsibility for determining if unblinding of a patient's treatment assignment is warranted for medical management of the event. The patient's safety must always be the first consideration in making such a determination. If the investigator decides that unblinding is warranted, it is the responsibility of the investigator to promptly document the decision and rationale and notify Lilly as soon as possible.

Upon completion of the study, all codes must be returned to Lilly or its designee.

7.4. Dose Modification

The patient should follow the planned dosing regimen. In the case of poor tolerability during the dose escalation phase of the study, dosing can be interrupted temporarily (Section 8.1.2 Temporary Interruption of Study Drug).

7.4.1. Special Treatment Considerations

Plasma glucose values will be measured daily at fasting by the patient using the BG meter provided during the lead-in period, after the eligibility is confirmed. Additional SMPG

measurements may be required, if needed, and will be agreed between the patient and the investigator or her/his designee.

7.4.1.1. Management of Hypoglycemia

To reduce the risk of hypoglycemia during the study, patients who have experienced more than 1 episode of severe hypoglycemia, as defined by the American Diabetes Association criteria in the 6 months prior to screening, who have a history of hypoglycemia unawareness or poor recognition of hypoglycemic symptoms, or who cannot communicate an understanding of hypoglycemic symptoms and the appropriate treatment of hypoglycemia prior to the first dose of study drug, will not be enrolled in the study.

If spontaneous hypoglycemia occurs, each episode will be treated according to the standards of care by the investigator and additional monitoring of glucose levels may be requested at the investigator's discretion (American Diabetes Association 2018). If an adjustment in treatment regimen would be needed to address increased frequency of hypoglycemia after randomization, the dose of metformin must be first reduced or, if clinically appropriate, metformin can be discontinued.

Should severe hypoglycemic episodes with coma, seizure, or neurologic impairment occur at any time, the patient may be treated with intramuscular/SC glucagon and/or concentrated intravenous (IV) glucose and will be discontinued from the study. Sustained carbohydrate intake and observation may be necessary because hypoglycemia may recur after apparent clinical recovery.

For management of hypoglycemia during the clamp procedures, see Section [7.4.1.3](#) (Treatment of Hypoglycemia during Hypoglycemic Clamp).

For hypoglycemia reporting, see Section [9.2.2.2](#) (Hypoglycemia).

7.4.1.2. Management of Hyperglycemia

If SMPG records indicate that PG values are exceeding the limits for severe, persistent hyperglycemia described in Section [9.2.2.3](#) (Severe, Persistent Hyperglycemia), and no intercurrent cause of the hyperglycemia is evident, rescue medications should be considered at the next scheduled clinic visit. The patient will be prescribed a rescue medication that does not interfere with study measurements. Acceptable rescue medications are listed in Section [7.7](#) (Concomitant Therapy). Patients who initiate rescue medications will be advised to follow appropriate national and international standards of care for management of diabetes, including applicable glycemic targets and SMPG schedule.

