Study Period Day	-14 ±3 ^a or -42 ±3 ^a	-7 ±3 ^a or -35 ±3 ^a (prior to randomization)	1	1	Patients on metformin only should perform Visits 1 and 2 approximately 2 and 1 week prior to Visit 3. Patients on metformin and one additional OAM should perform Visit 1 about 6 weeks prior to Visit 3, in order to permit eligibility assessment at Visit 2. OAMs other than metformin will be discontinued immediately after Visit 2 followed by at least 4-weeks washout between Visit 2 and Visit 3.
Diagnostics					
PK sample			P	P	PK and immunogenicity to be time-matched as much as possible.
Immunogenicity			P	P	
Pharmacogenetic sample			P		Single sample taken predose on Day 1 Period 1.
Nonpharmacogenetic stored samples			P	P	Fasting sample.

Abbreviations: AE = adverse event; BP = blood pressure; ECG = electrocardiogram; FSH = follicle-stimulating hormone; P = predose; PK = pharmacokinetic; PR = pulse rate; SMPG = self-monitoring of blood glucose.

a Visit windows are relative to randomization (Period 1, Day 1).

b A serum pregnancy test will be taken during Visit 2 if the FSH ≤40mIU/mL at Visit 1.

Note: If multiple procedures take place at the same time point, the following order may be consulted for prioritization: ECG, vital signs, counter-regulatory hormone samples, safety laboratory tests, PK samples, immunogenicity samples, storage samples.

Study Schedule Protocol I8F-MC-GPHG: Treatment Periods 1 and 2

Procedure	Treatment Periods 1 and 2												Comments		
Visit Period 1	4	5		6			7			8	9	9			
Visit Period 2	11	12		13			14			15	16	16			
Study Period Week	2	3	4	5	6	7	8	9	10	11	12	12			
Study Period Day	8 ±1	15 ±1	22	29 ±1	36	43	50	57 ±1	64	71	78 ±2	79 ±2	80 ±2	Patients should attend on stated day. When the patient is unable to attend CRU on the stated day, visit windows should be used for dosing only. Days 78, 79, and 80 should occur consecutively, without interruption.	
Weight				P			P			P					
Vital signs (BP/PR/body temperature)	P	P		P			P			P	X See Appendix 6		Refer to screening table.		
ECGs				P						P	X See Appendix 6		Refer to screening table.		
Concomitant medications	X														
AEs	X														
Physical examination / medical assessments	X									X			Refer to screening table.		
Alcohol breath test											X				
CRU admission											X				
CRU discharge												X			
Outpatient visit	X	X		X			X			X					
Dispense study treatment		X		X			X						For outpatient use.		

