5.1.2. Treatment

The tirzepatide treatment period will consist of a step-wise dose escalation. The starting dose will be 2.5 mg QW for 2 weeks, followed by an increase to 5 mg QW for 2 weeks, and 10 mg QW for 4 weeks until the 15-mg dose is reached and maintained for the remainder of the treatment period (4 weeks), see Section 5.5 (Justification for Dose) for further details. Patients will visit the clinical research unit (CRU) as outpatients 1 week after administration of the first dose (Week 2) and for administration of the first of each escalated dose during both the tirzepatide and placebo treatment periods (Weeks 3, 5 and 9 of each treatment period). Study drug will be dispensed to the patient at these visits for self-administration on all other dosing days. Telephone visits will be conducted to ensure that outpatient dosing occurs and to monitor safety.

The schedule of clinic visits and study procedures during the treatment periods, including sampling for immunogenicity and pharmacokinetic (PK) assessments, are provided in Section 2 (Schedule of Activities).

Patients will attend the CRU as outpatients on Week 12 of each treatment period to receive the final dose of study drug. The following day, patients will be admitted to the CRU and will undergo a hypoglycemic clamp procedure as detailed in Appendix 6.

Patients who initiate rescue medication for treatment of severe hyperglycemia (Section 7.4.1.2 Management of Hyperglycemia) during the study may continue in the study but rescue medication will be discontinued 1 week before the clamp procedure to avoid interference with measurements planned during the hypoglycemic clamp.

Patients who permanently discontinue study treatment early, irrespective of the reason, will be discontinued from the study (Section 8.1 Discontinuation from Study Treatment). They will perform an early termination (ET) visit as soon as possible after the decision to discontinue study treatment, followed by a safety follow-up visit up to 4 weeks later.

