The allowed rescue medications in the case of severe, persistent hyperglycemia after randomization are insulin and sulphonylureas. The preference should be given to the use of insulin, with sulphonylurea to be considered only if the patient is not willing to initiate insulin therapy. The sodium-dependent glucose co-transporter-2 (SGLT2) inhibitors should not be used because of possible interference with regulation of glucagon secretion. The GLP-1 RAs and dipeptidyl peptidase IV inhibitors should not be used because these classes of agents share the same mode of action pathways with dual GIP/GLP-1 RAs. Patients will be required to discontinue rescue medications 1 week prior to the clamp procedures.

After the completion of the treatment periods, patients can receive other glucose-lowering agents, except GLP-1 RAs.

Weight-Lowering Medications

Section 6.2 (Exclusion Criteria) provides requirements regarding prescription drugs that promote weight loss prior to entry and during the screening/lead-in period. Prescription or over-the-counter medications to promote weight loss are not allowed after randomization. If used ≤ 14 days, the patient will be required to discontinue this treatment and continue in the study. If used > 14 days after randomization, the patient will be immediately discontinued from the study drug and will perform end-of-study procedures (ET visit and safety follow-up within 4 weeks). If prescription or over-the-counter medications to promote weight loss are used, this will be considered a protocol deviation.

Corticosteroids

Section 6.2 (Exclusion Criteria) provides requirements regarding the use of chronic systemic glucocorticoids prior to entry and during the screening/lead-in period. Patients treated with systemic glucocorticoid therapy after randomization for > 14 consecutive days (with the exception of topical, intra-articular, and inhaled preparations) will be discontinued from the study. If used ≤ 14 days, the patient will be required to discontinue this treatment and continue in the study.

Other Medications

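### Tying rescue to the next scheduled clinic visit leaves two stretches of each treatment period (Day 29 to 57 and Day 57 to 78) with no scheduled point at which to act on the protocol's own hyperglycemia limits

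*Protocol*

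**What the plan says.** All references are to the Protocol.

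- **Limits.** Section 9.2.2.3 sets the rescue criteria on average fasting plasma glucose over any two weeks: above 270 mg/dL from Day 1 to the end of Week 6, and above 240 mg/dL from Week 7 to the end of Week 12.
- **When to act.** If the home records pass these limits with no intercurrent cause, Section 7.4.1.2 says "rescue medications should be considered at the next scheduled clinic visit".
- **Clinic visits.** Section 5.1.2 places outpatient visits in Week 2, at the first dose of each escalation step ("Weeks 3, 5 and 9 of each treatment period"), and in Week 12. In the Schedule of Activities these are Days 8, 15, 29, 57 and 78.
- **Run-up to the clamp.** The Schedule adds that "Days 78, 79, and 80 should occur consecutively, without interruption".
- **Rescue stop.** Section 5.1.2 says "rescue medication will be discontinued 1 week before the clamp procedure to avoid interference with measurements planned during the hypoglycemic clamp". Section 7.7 repeats it: "Patients will be required to discontinue rescue medications 1 week prior to the clamp procedures".
- **Rescue drugs.** Section 7.7: "The allowed rescue medications in the case of severe, persistent hyperglycemia after randomization are insulin and sulphonylureas". It does not limit their start to a clinic visit.
- **Data and calls.** Section 7.4.1: "Plasma glucose values will be measured daily at fasting by the patient". Section 5.1.2: "Telephone visits will be conducted to ensure that outpatient dosing occurs and to monitor safety".
- **Washout.** The washout schedule has no visit number. Its footnote defers review of home glucose to the first-dose visit of Period 2.

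**The concern.** The protocol defines a level of hyperglycemia at which it wants rescue considered, then ties that decision to a visit calendar built around dose escalation. The calendar is sparse in the second half of each period. In the last stretch it also collides with the pre-clamp rescue stop: the visit to which the patient is referred falls after the last day on which rescue could be used.

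Patients record a fasting value every day, but the diary is scheduled for review only at clinic visits. No text asks for the two-week average to be checked at a telephone visit. At stake is avoidable time above the sponsor's own limit, on days when treatment was still allowed.

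**Working it through.** The plan states no figure for this delay, so there is none to reproduce. The check is calendar arithmetic on nominal days.

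**Inputs.** Clinic visits on Days 29, 57 and 78 (Section 5.1.2, Schedule of Activities). Clamp run-in on Day 79 and hypoglycemic induction on Day 80 (Appendix 6). Rescue off one week before the clamp (Sections 5.1.2, 7.7). Week 6 ends on Day 42 and Week 7 starts on Day 43. Let *q* be the first day on which a full 14-day window exceeds the limit.

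**Length of the gaps.**
- Day 29 to 57: 57 − 29 = 28 days (26 to 30 with the ±1-day windows).
- Day 57 to 78: 78 − 57 = 21 days (76 − 58 = 18 to 80 − 56 = 24 with windows).

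**Rescue stop.** 79 − 7 = Day 72, or 80 − 7 = Day 73, depending on which day counts as the clamp. The last usable rescue day is Day 71 or 72.

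**First gap (above 270 mg/dL).** The wait is 57 − *q*. The 14-day window starts on Day *q* − 13, so the Day 29 review already holds 29 − (*q* − 13) + 1 = 43 − *q* of its values.

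| *q* | Wait to Day 57 | Values held at Day 29 |
|---|---|---|
| 30 | 27 days | 13 of 14 |
| 36 | 21 days | 7 of 14 |
| 42 | 15 days | 1 of 14 |

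**Second gap (above 240 mg/dL).** The earliest full window from Day 43 ends on Day 43 + 13 = Day 56, so Day 57 is the only scheduled clinic visit at which this criterion can lead to rescue before the stop. For *q* from Day 58 on, the wait to Day 78 is 78 − *q*. Of this, 72 − *q* to 73 − *q* days are permitted rescue lost to the visit wording. The other 78 − 73 = 5 to 78 − 72 = 6 days come from the rescue-free rule and are not part of this point. Values held at Day 57: 57 − (*q* − 13) + 1 = 71 − *q*.

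| *q* | Wait to Day 78 | Permitted rescue days lost | Values held at Day 57 |
|---|---|---|---|
| 58 | 20 days | 14–15 | 13 of 14 |
| 64 | 14 days | 8–9 | 7 of 14 |
| 71 | 7 days | 1–2 | 0 of 14 |

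**What a check at an existing call would recover.** The telephone row of the Schedule is broken in the text I have, but one call appears to fall at about Day 64. A check there catches *q* = 58 to 64, which is 7 of the 14 or 15 affected days, and leaves 72 − 64 = 8 to 73 − 64 = 9 days of usable rescue. Patients with *q* = 65 to 71/72 need an unscheduled contact and gain at most 7 to 8 days, falling to 1.

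**Washout.** Days 81 to 135 give 135 − 81 + 1 = 55 days, and up to Day 149 gives 69 days, with no scheduled contact. The Section 9.2.2.3 criteria have ended by then.

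**The case against.** The strongest reply is that the text is permissive. Rescue is to be *considered* at the next visit, and nothing tells the investigator to wait for it. Section 3.3 promises regular glucose monitoring outside the clamps and leaves rescue to the investigator's discretion. Section 7.7 allows rescue after randomization with no visit limit, and short-term insulin for acute conditions. Sections 5.1.1 and 7.4.1 allow extra home measurements. Section 9.2 makes the investigator responsible for medical care throughout. Severe, persistent hyperglycemia is an adverse event of special interest, so a safety call already covers it in principle. The patients with the longest waits have most of their high values in hand at the preceding review. The screening HbA1c caps (9.0%, or 8.5% with a second oral agent) suggest few cases, and the documents give no frequency.

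All of this stands as a limit on size: the delays above are upper bounds. It does not close the gap. Discretion helps only if someone sees the data, and what is missing is a scheduled look between visits. The one timing rule that Section 7.4.1.2 does state points to a visit that, after Day 57, comes too late.

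One might also object that earlier rescue brings treatment nearer the clamp. The one-week stop is unchanged, so no rescue would be given on a day the protocol does not already allow.

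On the washout, placebo-first patients undergo no change in active treatment, and former users of a second oral agent have already spent at least four weeks on metformin alone under surveillance (Section 5.1.1). The residual group is mainly tirzepatide-first patients whose second agent was withdrawn. That is why this part is optional.

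**Conclusion.** The point holds as a low-cost patient-safety improvement. Taken literally, Section 7.4.1.2 defers action by 15 to 27 days for a first breach of 270 mg/dL on Day 30 to 42. For a first breach of 240 mg/dL on Day 58 to 71/72 it refers the patient to a visit at which rescue can no longer be used before the clamp, at a cost of up to 14 to 15 permitted rescue days.

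This assumes nominal visit days, daily fasting values, and 14-day windows lying wholly inside the week ranges of Section 9.2.2.3. The call at about Day 64 is inferred from a damaged table.

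A reader might infer three stronger claims, and the documents support none of them:
- *Rescue is prohibited between visits.* It is not; Sections 3.3 and 7.7 leave it open.
- *The primary glucagon comparison is compromised.* Neither the gap nor the fix changes the rescue-free week, the clamp or the model.
- *Patients cannot be treated in the washout.* Section 7.7 exempts rescue after randomization from its medication ban. What is absent there is a criterion and a scheduled contact.

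**What to change.** **Main change.** In Section 7.4.1.2, have rescue considered at the next scheduled contact, clinic or telephone, or at an unscheduled visit if the limit is exceeded earlier. Add to the existing telephone visits a check of the two-week fasting average against Section 9.2.2.3. Keep the one-week rescue-free rule and the clamp schedule as they are. The cost is one changed phrase, a short check on calls the site already makes, and slightly more patients identified for rescue.

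**Optional.** Add one mid-washout telephone review of home glucose that applies the existing 240 mg/dL criterion, mainly for tirzepatide-first patients whose second oral agent was withdrawn. State that any washout rescue stops before the fasting glucagon, insulin and C-peptide samples on Day 1 of Period 2, because SAP Section 6.3 uses these as period baselines. The length of that rescue-free interval is for the sponsor to set. The cost is at most 38 × 1 = 38 calls, fewer if limited to the group named.
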